4. SUBJECT SELECTION

We aim to consent up to 100 women. Because we anticipate that approximately 20% will not meet eligibility criteria during the screening phase, this will achieve our accrual goal of 80 women (~40/treatment arm) who will complete the protocol and provide usable data for the acute primary outcomes. We also expect to have at least 72 women complete the 30-day follow-up period. These estimates derive from our experience with similar types of studies and populations.

Sources of recruitment: We will recruit study participants via several key resources that exist within our health system, including:

- RALLY, an online platform that serves as a resource for disseminating research opportunities within the Mass General Brigham (MGB) health system.
- The MGB-wide Research Patient Data Registry (RPDR), a research registry that allows investigators to query eligible participants based upon specified inclusion/exclusion criteria.
- Patient Gateway letters (identified via RPDR, described above). If we do not receive a response to our first letter within one week, we will send a second letter; if there is still no response, our third and final letter will be sent at least two weeks after the first. Following that, we will call up to three times, and if we are still unable to reach the patient, we will mark them as not interested. Patients who opted out will be filtered out of the recruitment list and they will not be sent the Research Invitation. The PI will conduct ongoing monitoring of patient responses to ensure that our selection criteria are identifying the right patients, and complaints about this method of recruitment will be submitted to the IRB as an other event.
- Relationships with clinical leadership of the Departments of Psychiatry, Obstetrics and Gynecology, and the Division of Women's Health within the Department of Medicine.

- Partnerships with colleagues at primary care and gynecology outpatient community clinics, and with Community Health Centers throughout the greater Boston area.

To optimize our ability to reach a broad, diverse population in the Boston area, we also plan to use targeted advertisements on social media (e.g., Facebook, Instagram). Recruitment ads will be posted from our research lab's social media account, and staff will not interact with potential subjects via social media. If anyone asks questions through social media, staff will only respond with "Please reach out to a study coordinator for more information" with a link to the participant-facing webpage (IRB-approved text). This response will come from the research lab's account, not any staff's personal accounts. Consistent with procedures in ongoing protocols, we will use culturally sensitive targeted enrollment techniques to ensure minority participation. These approaches include cultural competency training available from our institution, engagement with potential participants by providing educational materials, and responsiveness to participants' needs (e.g., flexible scheduling for outpatient procedures). All patient-facing recruitment materials will be approved by the IRB prior to distribution.

Inclusion and Exclusion Criteria:

Eligible participants will be stratified by use of psychotropic medication to treat depression.

Inclusion Criteria:

1. Healthy women ages 40 to 60 years
2. Perimenopausal, determined clinically per Stages of Reproductive Aging Workshop (STRAW) +10 criteria
3. Depressive symptoms, as determined by Hamilton Depression Rating Scale-17 score >20
4. Current use of psychotropic medications is allowed if the following applies:
 - The dose of psychotropic medications or other centrally acting medications is stable and expected to be unchanged within the 14 days prior to screening, and
 - It is expected that the dose of the psychotropic medications will not change before the completion of the 4-night inpatient stay
5. Able to read Arabic numerals and perform simple arithmetic
6. Able to provide written informed consent

Exclusion Criteria:

Medications:

1. Current or recent use of systemic hormone therapy
2. Centrally active medications (e.g., opiates, benzodiazepines) expected to be sedating, may significantly interfere with study outcomes, and/or interact with brexanolone, as judged by study investigators

Psychiatric and health history:

3. Other psychiatric illness that are considered to be primary (comorbid conditions are allowed)
4. Depression symptoms judged by the investigators to be too severe for study participation
5. Current suicidal ideation (Columbia Suicide Severity Rating Scale, C-SSRS)
6. Current or recent substance use disorders
7. Medical conditions or treatments that preclude Peri determination
8. Obstructive sleep apnea
9. Other sleep conditions
10. Other medical conditions: pregnancy, lactation, auto-immune disorders, neurological disorders or any condition that might confound the diagnosis and/or interpretation of study data
11. Abnormal hepatic and renal function
12. Known allergy to progesterone, exALLO, or brexanolone
13. History of head injury resulting in loss of consciousness > 20 min

Other:

14. Inability to comply with barrier contraceptive methods
15. Intellectual disability
16. Investigator judgement that study participation will constitute substantial risk given medical or psychiatric condition

17. Current or recent participation in clinical trial involving experimental therapy judged by investigator to interfere with risk of or interpretation of data from our protocol
18. Inability to comply with study procedures
19. Inability to communicate in English

Additional exclusions for optional magnetic resonance imaging (MRI):

20. Medical contraindications to MRI (e.g., aneurysm clip, pacemaker)
21. Medical conditions that would interfere with MRI protocol or data interpretation (e.g., neurologic, cardiac, or pulmonary disease incompatible with lying flat for >90 min)
22. Claustrophobia or abnormal movements sufficiently severe to interfere with MRI scan

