2. SPECIFIC AIMS AND OBJECTIVES

We propose to test the effects of exogenous ALLO in a well-characterized cohort of women with mild to severe depression presenting during early and late perimenopause. This project will use an experimental placebo-controlled, mechanistic trial to determine acute and durable effects of exogenous ALLO on behavioral, cognitive, circuit-level, physiological, and molecular processes centered on the Negative Valence Systems and Arousal and Regulatory Systems Domains of the Research Domain Criteria (RDoC) framework. We expect to uncover neurobiological mechanisms that underlie depression during early and late perimenopause via three aims:

Aim 1: To determine the impact of allopregnanolone on key behavioral and circuit-based processes that underlie depression in perimenopausal women.

Hypotheses: Compared to placebo, exogenous ALLO will improve the following: **1a) behavioral/cognitive** measures of rumination and attentional bias toward negatively valenced external stimuli; and **1b) neurocircuitry**, via resting-state connectivity underlying rumination and negative attentional bias within the default mode network and between the default mode and salience networks.

Aim 2: To determine the impact of allopregnanolone on key molecular and physiological processes that underlie depression by indexing markers of neuroprotection, peripheral inflammation, and sleep physiology in perimenopausal women.

Hypotheses: Compared to placebo, exogenous ALLO will improve the following: **2a) neuroprotection**, via circulating levels of brain-derived neurotrophic factor (BDNF), and levels of N-acetyl-aspartate (NAA) in the medial prefrontal cortex, measured with magnetic resonance spectroscopy; **2b) inflammation**, via circulating levels of pro-inflammatory molecules; and **2c) sleep physiology**, via EEG-derived wakefulness after sleep onset.

[figure not shown]
Exploratory Aim 3: To identify mediators and moderators of the impact of allopregnanolone on clinically-defined global measures of depression severity in perimenopausal women.

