The primary analyses to test the hypotheses listed in Aims 1 and 2 will compare allopregnanolone and placebo subject-level response profiles from baseline to 4-day visit for each primary outcome using linear or generalized linear mixed models. Estimation of the fixed effects will allow comparison of means. Fixed effects will include treatment condition and time (baseline, 4-day, 30-day). Subject-level random effects will be modelled by including a random intercept. While linear or generalized linear mixed models provide a robust approach to handling inter-individual variability in response, we will also incorporate additional exploratory analyses to address this concern. To achieve this, we will examine our data using the interclass correlation coefficients (ICC) obtained from the R correlation matrix of the mixed-model regressions. A low ICC value will indicate that intra-individual variability in response is high relative to inter-individual variability, whereas a high ICC value will indicate that there is high inter-individual variation in response relative to intra-individual variability. Additionally, we will estimate subject-specific effects (i.e., slopes in response profiles of each subject from baseline to day 4, estimated by the random effect in the mixed models) and the distribution of subject-specific response magnitude. As exploratory analytic approaches, these subject-specific response magnitudes will be further modelled using baseline participant characteristics (e.g., age, prior history of depression) to elucidate potential physiological and neurophysiological predictors. We expect that these additional exploratory analyses will provide preliminary data on the distribution of participant-specific responses to ALLO, which will inform future studies and analyses. For **Aim 3**, the objective is two-fold: (1) we will assess mediation of improvement in clinically-defined global measures of depression severity by changes in Aim 1 and 2 outcomes, and (2) test effect modification of exogenous ALLO on improvement in clinically-defined global measures of depression severity by (i) the presence/absence of a history of depression recurrence, and separately, ii) perimenopausal factors (early vs. late perimenopause). In addition to the mediation pathways described above, we recognize that the possible pathways linking ALLO to depression are likely more numerous than these predefined mediation pathways. Therefore, we plan to further explore other putative pathways using partial least squares structural equation modeling. We will identify combinations of variables (features) that cluster together (factors) as latent variables, and then quantify the strength of their relationships based on factor loading (correlation between each feature and each factor). We will develop primary mediation models for 4-day effects and then 30-day secondary effects in

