The proposed sample size (n=80; 40 per arm) will yield more than 80% power to detect effect sizes 0.64 or larger in a two-tailed, two-sample contrast of group-level means, consistent with our primary analysis plan to assess acute treatment effect (4-day) of exogenous ALLO compared to placebo. Furthermore, this approach avoids a priori presumptions to be made on data distribution and impact of potential covariates (i.e., linear vs. non-linear relationship with the outcome). We conservatively based our anticipated estimates on published effect sizes for progesterone-associated or ALLO-induced changes in behavioral, circuit-based, molecular, and physiological measurements of the RDoC Negative Valence System and Arousal and Regulatory System domains, and when none were available, on our own pilot data. While the sample size justification uses a cross-sectional approach as if there is one measurement per participant, the data and analyses will be longitudinal – accounting for repeated measured per participant, which also will increase power and precision. Therefore, we expect that this mixed-model analytic approach will yield even greater statistical power than the conservative estimates from the simpler approach used for sample size determination.

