For all primary contrasts, effect sizes estimated from either previous reports or our own preliminary data were large ($d \geq 0.8$). Specifically, for **Aim 1**: the effect of progesterone on rumination assessed using MADRS Item 9 (Pessimistic Thoughts) and the Beck Depression Inventory (BDI) subscore from Items 5 and 8 (Guilt and Self-incrimination, respectively) were large (Cohen's $d > 0.95$), an effect size that is consistent with previously reported⁴⁸, effects of exogenous ALLO on depression symptom ratings using the HDRS-17 being large (Cohen's $d > 1$), as will be investigated in **Aim 3**. Progesterone's effects on attentional bias to negative stimuli as well as functional connectivity are estimated from our preliminary data to be large ($d > 1$). **Aim 2**: Progesterone's effects are estimated from our preliminary data to be large on both BDNF and the inflammation index (derived from CRP, TNF- α , and IL-6 levels) ($d \geq 0.8$). Effects of progesterone on NAA levels in the medial prefrontal cortex, estimated from our preliminary data, and EEG-derived WASO, estimated from a previous report⁴⁹ of exogenous progesterone on sleep parameters in postmenopausal women, are both large ($d > 1$). For Aim 3: Based on prior reports and our preliminary data, our sample size (n=80; 40 per arm) will yield more than 80% power to detect select mediation as identified above.

10. Monitoring and Quality Assurance

This mechanistic intervention study will be conducted as a single-site inpatient randomized placebo-controlled trial using an agent that is FDA approved for women with a hormonally based depression in a new population of women who also have a hormonally based depression. The dose and method of administration—60-hour infusion of brexanolone—will be identical to the marketed agent. Research participants will be closely monitored for adverse events by physicians and nurses in the CCI research unit and by our experienced investigative team, which together participated as a site for the Sage Therapeutics PPD Phase 2 clinical trials using SAGE-547 (now FDA-approved as brexanolone). To minimize risks during the infusion, the FDA-approved Risk Evaluation and Mitigation Strategy (REMS) for brexanolone¹ will be strictly adhered to by our hospital clinical staff on the IPM Unit, consistent with procedures we implemented during the SAGE-547 trial. Safety monitoring will include frequent nursing checks, continuous oxygen saturation by pulse oximetry monitoring, and

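### The single statement of n=80 and detectable d=0.64 does not carry over to connectivity (1b) and mPFC NAA (2a), which depend on optional MRI with no stated n

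*Combined protocol and SAP*

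**What the plan says.** **One n and one detectable effect.** Section 4 (Subject Selection) sets the accrual goal as "80 women (~40/treatment arm) who will complete the protocol and provide usable data for the acute primary outcomes". Section 9 (Statistical Analysis) states: "The proposed sample size (n=80; 40 per arm) will yield more than 80% power to detect effect sizes 0.64 or larger". It ties this to a two-tailed, two-sample comparison of means for the 4-day effect. Neither place makes an exception for imaging.

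**Imaging outcomes are among the primary ones.** In Section 2, hypothesis 1b concerns "resting-state connectivity underlying rumination and negative attentional bias within the default mode network and between the default mode and salience networks". Hypothesis 2a includes NAA "in the medial prefrontal cortex, measured with magnetic resonance spectroscopy". Section 9 says: "The primary analyses to test the hypotheses listed in Aims 1 and 2 will compare allopregnanolone and placebo subject-level response profiles". Its list of anticipated effects for the primary contrasts covers both. Progesterone's effects on "attentional bias to negative stimuli as well as functional connectivity are estimated from our preliminary data to be large" (d>1), and "Effects of progesterone on NAA levels in the medial prefrontal cortex, estimated from our preliminary data" are also given as d>1.

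**MRI is mostly described as optional.**
- Section 4 has three exclusions (20 to 22) that apply only to the optional MRI.
- Section 6 labels the pre-admission, post-admission and follow-up scans optional.
- The remuneration list pays for MRI visits only if the woman is MRI eligible.
- The Table of Procedures groups the scans under optional imaging.

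**Two places read differently.** Section 3 describes MRI as something participants have, and calls only the MRS sequences optional. The MRI item under Protections Against Risk in Section 7 says that women with certain implants might be unable to take part in the study at all.

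The documents give no expected MRI uptake, no number with usable scans and no MRI-specific power figure.

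**The concern.** As the criteria are written, a woman with a pacemaker or severe claustrophobia can be randomized and never scanned. She counts toward the 80 but contributes nothing to connectivity or NAA. Hypothesis 1b has no measure other than MRI. The number available for these two outcomes is therefore at most 40 per arm and probably lower, yet the only sensitivity figure in the plan is calculated at 40 per arm.

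What is at stake is how a null result is read. The anticipated d>1 for both outcomes comes from preliminary data on progesterone, not brexanolone. If the true effect is smaller, a reader of a null finding on 1b or NAA needs to know what the scanned subset could have detected. The plan's figure would tell that reader 0.64, which holds only if essentially everyone has usable scans.

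**Working it through.** **Inputs from the documents.** 40 per arm, d=0.64, two-tailed two-sample comparison, power above 80% (Section 9, sample size); alpha 5% per test (Section 9, Analysis Plan); 1:1 allocation (Section 5); anticipated d>1 for connectivity and NAA (Section 9).

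**Input assumed.** The share of women with usable scans is not in the documents. I take 50 to 100% of 40 per arm, split equally between arms.

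**Formula.** For n per arm, the two-sided t-test has 2n−2 degrees of freedom and noncentrality d·√(n/2). Power is the probability that a noncentral t variable exceeds the 97.5% point of the central t. The FDR step is not included, as in the plan's own calculation.

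**Step 1: reproduce the plan's figure.** At n=40, the noncentrality is 0.64·√20 = 2.862 and the critical value is 1.991 (78 df). Power is 80.7%, and the detectable d at 80% power is 0.634. The plan's figure reproduces.

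**Step 2: look for slack.** At n=39, the noncentrality is 0.64·√19.5 = 2.826 and power is 79.7%. Losing one woman per arm takes power just below the stated level.

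**Step 3: smaller scanned subsets.**

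| Assumed uptake | n per arm | Detectable d (80% power) | Power at d=0.64 | Power at d=1 |
|---|---|---|---|---|
| 100% | 40 | 0.63 | 80.7% | 99% |
| 90% | 36 | 0.67 | 76.4% | 99% |
| 80% | 32 | 0.71 | 71.2% | 98% |
| 70% | 28 | 0.76 | 65.2% | 96% |
| 50% | 20 | 0.91 | 50.5% | 87% |

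At d=1, power is 80.7% with 17 per arm and 78.1% with 16. Seventeen of 40 is 42.5% uptake.

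**Step 4: the longitudinal gain.** Section 9 says of its own method: "While the sample size justification uses a cross-sectional approach as if there is one measurement per participant". It expects the repeated-measures model to do better, but gives no correlation. The size of the gain, and whether there is one, depends on how baseline enters the model. Let ρ be an assumed correlation between baseline and day 4, with equal variances.
- Baseline adjusted for, or constrained equal between arms: effective d = 0.64/√(1−ρ²), with one degree of freedom lost.
- Difference in change with baseline means free by arm: effective d = 0.64/√(2(1−ρ)).

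| Assumed ρ | Effective d, adjusted | n per arm for 80% | Effective d, change | n per arm for 80% |
|---|---|---|---|---|
| 0.3 | 0.671 | 36 | 0.541 | 55 |
| 0.5 | 0.739 | 30 | 0.640 | 40 |
| 0.6 | 0.800 | 26 | 0.716 | 32 |

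Section 9 describes a random-intercept mixed model of response profiles, with baseline as one of the modelled time points. It does not specify baseline adjustment. Under the change contrast, ρ=0.3 needs more women than the cross-sectional test, and ρ=0.5 gives no gain.

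**The case against.** **The anticipated effects are large, so nothing is lost.** This is the strongest reply, and most of it stands. At d=1 the imaging outcomes keep 87% power even at half uptake. A reader might infer from the table that connectivity and NAA are underpowered. The documents do not support that: at the effect the plan anticipates, planned power is lost only below 17 per arm. What remains is that the plan also chose to state a sensitivity of 0.64, and that figure is not secured for these outcomes.

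**The calculation is right.** It is. A reader might take this point as an arithmetic error in the sample size; it is not. The figure is correct at 40 per arm and is applied to outcomes whose n is not given.

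**The mixed model will make up the difference.** It may, if baseline is adjusted for or constrained equal and the correlation is sufficient. It may equally fail to do so under a change contrast. The plan states neither the model detail nor a correlation, so the gain cannot be relied on or ruled out.

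**MRI may in fact be required.** Sections 3 and 7 can be read that way. If so, optionality is no longer the problem, and the wording in Sections 4 and 6 is what needs correcting. Unusable scans would still have to be allowed for.

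**The loss may be small.** At 90% uptake the detectable d is 0.67 against 0.63 at 40 per arm, which is slight. The documents do not say whether uptake will be that high.

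**Conclusion.** The point holds as one of stated sensitivity. On the plan's own cross-sectional calculation, d=0.64 at more than 80% power requires 40 women per arm, and the plan as written does not secure that number for connectivity or NAA. Over assumed uptake of 90 to 50%, the detectable d runs from 0.67 to 0.91, and power at 0.64 from 76% to 51%. These figures rest on an assumed uptake, an equal split between arms, a two-sided 5% t-test and no FDR adjustment.

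The viability of these hypotheses at the anticipated d>1 is not in question, and the n=80 calculation itself is sound. Nor does this vouch for 40 per arm on the behavioural, blood and EEG outcomes: Section 4 goes from about 20% screening loss straight to 80 usable, and the same lack of slack applies there. A correction is worth making because it is cheap and bears directly on how a null imaging result is interpreted.

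**What to change.** First reconcile the status of MRI across Section 3, the MRI exclusions in Section 4, the visit descriptions, remuneration list and Table of Procedures in Section 6, and the MRI item under Protections Against Risk in Section 7.

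- **If MRI stays optional:** do not apply the n=80, d=0.64 statement to connectivity and NAA. For each of the two, separately, give the expected number per arm with usable baseline and day-4 scans and the detectable effect at that number. If a longitudinal gain is relied on, state how baseline enters the model, the assumed correlation and the resulting figure.
- **If MRI is required:** correct the optional wording and allow for unusable scans in the stated n.

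The cost is text only, with no added participants or procedures. The stated figures for the imaging outcomes may become less favourable.

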5. SUBJECT ENROLLMENT

Pre-Screening: Recruitment materials will direct interested participants to an electronic prescreen survey on REDCap. This prescreen survey consists of questions related to eligibility, including the PHQ-8. If participants are likely to be eligible based on pre-screen questions, they will be asked to provide contact information and notified that research staff will reach out to them to schedule and conduct a telephone screen.

Telephone Screen: Potentially eligible participants will be screened over the phone to determine if they continue to meet inclusion/exclusion criteria. Verbal consent to complete the telephone screen will be obtained at the start of the phone call. Before research staff asks any screening questions, they will inform the potential participants that the purpose of the call is to begin the process of pre-screening for eligibility and that all responses are confidential and voluntary. Interested participants who prefer not to answer questions will be thanked for their time and the phone call will end. They may ask to stop the screening phone call at any time. All potential participants who appear eligible based on the pre-screen and telephone screen will be scheduled for a Screening Visit.

Informed Consent and Assent: Participants will not undergo any study procedures until they understand the risks and benefits and provide written and informed consent to participate. At part 1 of 2 of the screening visit, the consenting study physician will review the consent form in its entirety with prospective participants utilizing REDCap. The consent form will include information about the risks and benefits of study participation and contact information for the study investigators and research staff. The consent will include information about all study risks, including those related to the infusion of brexanolone or saline. Participants enrolling in the study must understand the nature of the study, the discomforts/risks, and potential benefits. Any questions or areas of concern regarding the protocol will be addressed. The participants may choose to have a confidant with them during the consent procedure. If potential participants feel comfortable with the study procedures, they and the study physician will sign the consent form. Enrolled participants will be given a copy of the completed consent form before any study procedures are completed, and a copy of the signed consent form and documentation of the informed consent process will be stored in the participant's research file.

If participants have reservations about study participation at the first visit, they will have the option to take the consent form home to consider the decision to participate in the study and to consult with their family and health-care providers. They can return at a later date to discuss the study again before signing the consent form and initiating study procedures.

The study protocol, informed consent form, telephone and REDCap screens, and all other study procedures will be approved by the IRB before the study is initiated.

Double-blind Randomization: Subjects will be randomized 1:1 to brexanolone or saline infusion, stratified by use of psychotropic medication to treat depression status. Treatment allocation will be known only by the biostatistical consultant, Safety Monitoring Group, and BWH Investigational Drug Service, the latter of whom will determine the permuted block randomized assignment. Subjects and study staff will be blinded until primary analyses are done, unless unblinding is required for safety.

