- The 60-hour brexanolone vs placebo infusion will begin in the evening of the 2nd inpatient night and end on the last morning immediately preceding post-treatment assessments
- Safety assessments will be conducted daily throughout the infusion and inpatient stay
- 2 electroencephalography (EEG) recordings (one before infusion and one during the final night of the infusion)
- At least once daily assessments of rumination, attentional bias, psychomotor vigilance, mood state (POMS), and depressive symptoms (before and after the infusion)
- Daily blood draws (before and after the infusion). Blood will be collected to run assays, including brain derived neurotrophic factor (BDNF), inflammatory biomarkers, reproductive hormones, serum ALLO levels, and serum for future analyses.
- One urine collection at admission for HCG, one at morning void after first night for melatonin. If there happens to be overnight voiding on first night additional samples will be requested but there is no scheduled collection, it will only be done if the participant is awake to void on their own.

Optional post-admission MRI Visit: resting-state functional MRI (rfMRI) / magnetic resonance spectroscopy (MRS) scans (after the infusion)

Interim Follow-Up and Remote Visit: During the 1-month follow-up period after participants are discharged from the inpatient visit, participants will be asked to complete daily monitoring of their sleep, VMS, and menstrual cycle patterns.

One remote interim visit approximately 2 weeks after the inpatient visit will take place to monitor adverse events, administer the C-SSRS, and assess mood state (POMS) and depressive symptoms.

Follow-Up In-Person Visit: Approximately 30 days after treatment initiation, participants will have a final follow-up in-person visit, during which they will undergo:

- Adverse event and safety monitoring
- Optional rfMRI/MRS scanning procedures
- Behavioral assessments including depressive symptom severity, mood state (POMS), rumination, and attentional bias, psychomotor vigilance; and
- Blood draw for neuroprotective and inflammatory biomarkers, reproductive hormones, ALLO levels, and serum for future analyses.

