Analysis Plan: Briefly, primary analyses will compare exALLO and placebo subject-level response profiles from baseline to 4-day in each primary outcome to examine acute effects. Secondary analyses will compare exALLO and placebo subject-level response profiles from baseline to 30-day in those same outcomes to examine durability of effects. Analyses of secondary outcomes will be conducted in parallel with those for primary outcomes. Key covariates (e.g., age, race, body mass index, socioeconomic status and stressful events) will be measured and considered a priori as potential predictors in multivariate analyses to reduce unexplained variability. Analytic outcomes can be transformed as needed to satisfy model assumptions such as normally distributed residuals for linear models or, alternatively, non-linear distribution models (e.g., negative binomial, lognormal, or gamma) can be applied in the generalized linear mixed model approach to model the observed distribution of the outcome. Model selection will be based on Akaike information criterion or quasi-likelihood under the independence model criterion values. We will use the False Discovery Rate (FDR) correction⁴⁵, which allows for robust retention of alpha to remain at 5% for each statistical test with the additional constraint of q-threshold also set to 5% (i.e., acceptable FDR of 5%). This analytic approach is advantageous over Bonferroni adjustment and other approaches that adjust the 5% alpha threshold as it will not increase the chance of inflating Type II error given the number of primary outcomes in Aims 1 and 2.

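### Randomisation is stratified by psychotropic medication use, but the analysis plan does not commit to the stratum in the mixed models (minor, near-free improvement)

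*Combined protocol and SAP*

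**What the plan says.** The stratification is stated twice. Section 5 (Double-blind Randomization) has "Subjects will be randomized 1:1 to brexanolone or saline infusion, stratified by use of psychotropic medication to treat depression status", with permuted blocks set by the investigational pharmacy. Section 4 (Inclusion and Exclusion Criteria) has "Eligible participants will be stratified by use of psychotropic medication to treat depression". No other stratification factor is named.

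The model is in section 9 (Statistical Analysis). On fixed effects: "Fixed effects will include treatment condition and time (baseline, 4-day, 30-day". On random effects: "Subject-level random effects will be modelled by including a random intercept". On covariates: "Key covariates (e.g., age, race, body mass index, socioeconomic status and stressful events) will be measured and considered a priori as potential predictors". After the text on transformations and alternative distributions comes: "Model selection will be based on Akaike information criterion or quasi-likelihood under the independence model criterion values".

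The Aim 3 effect modifiers are history of recurrence and early versus late perimenopause, not the stratum. No section commits the stratum to any model.

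**The concern.** Stratified blocks balance the arms on medication use. The treatment estimate therefore varies less from trial to trial than it would under simple randomisation. A model without the stratum does not recognise this: any variance the stratum explains stays in the residual, and the standard error is overstated. The test is then conservative and the intervals are a little too wide.

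The protocol itself gives some reason to expect a link. Section 2 says SSRIs raise serum allopregnanolone and increase BDNF and NAA, and the last two are Aim 2 outcomes. That supports a difference in level between medicated and unmedicated women. A difference in change would be a further inference.

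Also at stake is pre-specification. With the stratum left optional, it could be in the model for one outcome and out for another.

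**Working it through.** **The plan's own figure.** Section 9 claims more than 80% power at d = 0.64 with 40 per arm, two-sided, with alpha 5%. The normal approximation is Φ(0.64·√(40/2) − 1.96) = Φ(2.862 − 1.960) = 0.817. The noncentral t with 78 df gives 0.807. The claim reproduces, and it contains no stratum term.

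**Inputs.** From the documents: 40 per arm, 1:1, d = 0.64 (detectable minimum) and d ≥ 0.8 (anticipated for all primary contrasts). Assumed, because no section gives it: R², the share of the variance of the tested change explained by the stratum, at 0, 2, 5, 10 and 20%. Also assumed: linear models, all 80 women analysed, and strata balanced between arms. The FDR step is not modelled.

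**Formulas.**
- True size with the stratum omitted: 2·(1 − Φ(1.96/√(1 − R²))).
- Excess interval width: 1/√(1 − R²) − 1.
- Power with the stratum included: noncentral t at d/√(1 − R²), 77 df.
- Power with it omitted: simulated two-sample t-test, 78 df, 200,000 trials.
- Difference in change between medicated and unmedicated women implied by R², with a 50/50 split: 2·√R² SD.

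| R² | Implied difference (SD) | True size | Interval excess | Power d = 0.64, omitted / included | Power d = 0.8, omitted / included |
|---|---|---|---|---|---|
| 0 | 0 | 5.0% | 0% | 80.7 / 80.7% | 94.2 / 94.2% |
| 2% | 0.28 | 4.8% | 1% | 81.0 / 81.5% | 94.4 / 94.6% |
| 5% | 0.45 | 4.4% | 3% | 81.3 / 82.6% | 94.7 / 95.2% |
| 10% | 0.63 | 3.9% | 5% | 81.8 / 84.6% | 95.1 / 96.1% |
| 20% | 0.89 | 2.8% | 12% | 83.3 / 88.5% | 95.9 / 97.7% |

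Example at R² = 10%: √0.9 = 0.949, so 1.96/0.949 = 2.066 and the two-sided size is 0.039. Simulation error in the omitted-power figures is about 0.1 to 0.2 points. A 20/80 split of the strata gives nearly the same result at R² = 10% (81.7 against 84.5% at d = 0.64).

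**When the loss is zero.** Section 9 compares response profiles from baseline to 4-day, which points to change as the tested quantity. A shift in level that is the same at both visits cancels in the change. With a 0.6 SD level shift and a within-subject correlation of 0.5 (both assumed), the mean standard error of the change contrast is 0.223 with or without the stratum. Section 9 does not, however, write out a treatment-by-time term. If arm means at day 4 were compared instead, a level shift would not cancel, and R² in the table would refer to the day-4 value.

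**Degrees of freedom.** With two strata the cost is 1 + (visits − 1). That is 3 for outcomes at baseline, 4-day and 30-day. It is 2 for WASO, because section 6 plans "2 electroencephalography (EEG) recordings (one before infusion and one during the final night of the infusion".

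**The case against.** The strongest reply is that this is a request for wording. The covariate list is introduced by e.g., the fixed effects are said to include treatment and time rather than to consist of them, and the stratum could be entered under the plan as written. That stands: what is missing is a commitment, and the plan does not exclude the analysis.

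The reply continues that the upper figures need a strong input. R² = 10% means a 0.63 SD difference in four-day change between medicated and unmedicated women, about the size of the smallest detectable drug effect, while section 4 requires stable doses through the inpatient stay. That also stands, and the realistic cost is probably near the bottom of the range. R² is nevertheless unknown, so the 10% row is not a ceiling.

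Three stronger readings are tempting, and the documents do not support them.
- *AIC/QIC will discard the stratum.* The model-selection sentence directly follows text on transformations and distributions, and most naturally governs distributional form. The plan does not say that it extends to covariates. A retention clause is only a precaution.
- *The stratum has a single level.* Section 7 (Potential Risks, Treatment delay) says women not on psychotropic medication for their episode will be enrolled, but it does not say only such women. Section 4 allows current use, section 5 stratifies by it, and section 7 (Protections Against Risk) says no washout is required. The sentence fits as a risk disclosure for the unmedicated women.
- *The trial is underpowered or its error rate inflated.* The table shows the reverse for error rate, and power stays at or above 80.7% in every row.

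**Conclusion.** The point holds as a minor one. The trial randomises within medication strata and does not commit to analysing by them. In linear models the consequence is conservative: for R² of 0 to 10%, true size is 5.0 to 3.9%, and the power forgone is 0 to about 3 points at d = 0.64 and 0 to about 1 point at d = 0.8. At R² = 20% it is about 5 and 2 points. No primary conclusion is put at risk.

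The size rests wholly on the assumed R². The figures do not cover the optional MRI outcomes (connectivity, NAA), where fewer women may contribute, or the non-linear models that section 9 permits. The case for acting is that the change costs almost nothing and fixes one more element of the primary model in advance.

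**What to change.** In section 9, state that the psychotropic-use stratum as randomised, with its interaction with visit, is a fixed effect in the primary and secondary mixed models. Add that it is kept whatever the AIC/QIC result, in case that selection is applied to covariates. Where the cells for optional MRI outcomes are too sparse, keep the stratum main effect alone. The plan for the other covariates need not change.

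Make the change before any outcome is analysed by arm. A cut-off of unblinding would not be clean, because section 5 says: "Treatment allocation will be known only by the biostatistical consultant, Safety Monitoring Group, and BWH Investigational Drug Service".

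As a separate wording note, clarify that the treatment-delay sentence under Potential Risks in section 7 describes the unmedicated women among those enrolled, or otherwise reconcile it with sections 4 and 5 and with the no-washout statement later in section 7.

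Cost: one or two sentences in section 9, a wording check in section 7, and 3 degrees of freedom per model (2 for WASO). The stratum is already recorded for randomisation. Sample size, visits and procedures are unchanged.
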